11.2 Analysis Populations**11.2.1 Safety Population**

The safety population will consist of all subjects who received at least one dose of each study drug and had at least one post-dose safety assessment. Safety summaries will include all subjects in the safety population.

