³ Includes: systolic and diastolic blood pressure, pulse rate, respiratory rate, and temperature.

⁴ Complete CBC including: hemoglobin, hematocrit, platelet and white blood cell count (WBC) with differential including circulating blasts and absolute neutrophil count.

⁵ BUN, creatinine, uric acid, total bilirubin, AST, ALT, alkaline phosphatase, LDH, sodium, potassium, calcium, magnesium, phosphorous, bicarbonate, chloride, glucose, albumin, and total protein.

⁶ Serum pregnancy test within 1 week of Cycle 1 Day 1 for females of childbearing potential. Repeat within one week prior to first day of each subsequent cycle.

⁷ Ciprofloxacin will be administered orally twice daily on Days 1 to 10 of a 28-day cycle.

⁸ Etoposide 200 mg will be administered orally once daily on Days 2 to 8 of a 28-day cycle.

⁹ The screening bone marrow assessment must be performed within 42 days of Cycle 1 Day 1 and must be reviewed at UF. If bone marrow analysis results from outside lab is used to confirm diagnosis, slides must be made available to be read by UF pathologist. This must confirm a diagnosis of AML, non-M3. In case of archived marrow used for eligibility or bone marrow inaspirable or slides unavailable to be read by UF pathologist, and there is greater than 10% blast present, peripheral blood may be collected for flow cytometry.

¹¹ Monitoring for SAEs and AEs starts the day patient signs the informed consent form (ICF), continuing throughout the study. Subjects who have received at least one dose of study drug and discontinue prematurely (regardless of reason) will be followed for any adverse events that occur during the study until 28 days (± 2 days) following the last dose of study treatment (i.e., the Follow-up Visit).

¹² End of treatment visit will occur at CID28 visit in subjects with progressive disease or at study withdrawal if the date does not correspond to a protocol-specified visit. Additional follow-up will include an assessment for the evaluation of AEs and concomitant medications 28 days (± 7 days) after the last dose of study medication. Other assessments will be performed as necessary by the treating physician.

¹³ All subjects will be followed monthly until: disease progression, death, or until 3 years from the on-study date.

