3.2.2 Ciprofloxacin

Ciprofloxacin is a quinolone antibiotic which works by inhibiting DNA gyrase (17, 18). Ciprofloxacin is a Topo II inhibitor and in-vitro and xenograft tumor models have shown that this drug has anti-proliferative and possibly pro-apoptotic activity (19-23) at concentrations ranging from 12-800 mcg/ML (19, 20, 23-27). The use of ciprofloxacin in the current trial is based on the ability of this drug to inhibit Metnase and thereby enhance the activity of etoposide in subjects with resistant acute leukemia. Hromas et al demonstrated that ciprofloxacin potentiated the activity of etoposide on AML cell lines at a concentration of 2 µmol/L (0.662µg/mL based on its molecular weight of 331) (4).

Per the prescribing information, a single dose of 250 mg, 500 mg, 750 mg, and 1000 mg of oral ciprofloxacin in healthy volunteers achieved a C_{max} of 1.2, 2.4, 4.3 and 5.4 µg/mL (28). The elimination half-life of ciprofloxacin is 4 hours, and PK studies have shown the mean serum concentrations at 12 hours after a single dose of 250 mg, 500 mg, and 750 mg were 0.1, 0.2 and 0.4 µg/mL, respectively.

The 750 mg twice daily as a starting dose was chosen because this dose results in sustained levels that approximate those shown to augment etoposide effect ([See Table 2](#)) (4). Further, this dose is commonly used for treatment of infection and has been well tolerated (28). To achieve a steady state concentration prior to initiation of etoposide, ciprofloxacin will be started 24 hours before etoposide is begun. If the starting dose of ciprofloxacin is tolerated, a higher dose of 1,000 mg twice daily will be explored in order to further increase ciprofloxacin 12 hour levels. Although less commonly used, this dose has also been well tolerated in studies in normal volunteers and in subjects with infection (29, 30).

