4.1 Etoposide and Ciprofloxacin

Ciprofloxacin will be administered orally twice daily on Days 1 to 10 of each 28-day cycle. Whenever possible, doses should be taken at 0800 hours and 2000 hours. If for some reason the doses are not taken at these times, ciprofloxacin can be taken as late as 6 hours after the scheduled time. If > 6 hours elapses, that dose of ciprofloxacin will be held and not made up. The starting dose will be 750 mg (dose level 0) with escalation to a maximum of 1000 mg (dose level +1) or de-escalation to a minimum of 500 mg (dose level -1).

Etoposide at a fixed dose of 200 mg will be administered orally once daily on Days 2 to 8 of each 28-day cycle. Subjects will be instructed to take etoposide with their morning dose of ciprofloxacin at 0800 hours on an empty stomach. If for some reason the dose is not taken at this time, it may be taken as late as 6 hours after the scheduled time. If >6 hours elapses, that dose of etoposide will be held and not made up.

A medication diary will be given to all subjects and they will be instructed to record the actual times they take both etoposide and ciprofloxacin. Doses missed will be recorded as such. Subjects will be told to call within 12 hours of missing a dose. Subjects will be instructed to bring the diary and any unused medication with them to all study visits. Any unused medication will be disposed of per institutional standard practice.

Subjects in Cycle 1 of Phase Ib who miss any etoposide or ciprofloxacin doses will be considered evaluable only if a DLT occurs. Otherwise they will be removed from the study on Day 28 and replaced in the cohort in which they were treated. Subjects in Phase Ib beyond the first cycle and those in Phase II will be considered evaluable for response if they have received at least one cycle in accord with the protocol. For these subjects non-compliance with dosing will be dealt with at the discretion of the PI.

Standard administration instructions will be given to each subject for ciprofloxacin (*e.g.*, separating administration from dairy products, calcium-fortified juices, sucralfate, antacids, or other medications that contain aluminum, magnesium, calcium, iron, or zinc). Subjects will be advised not to consume grapefruit or grapefruit juice within 7 days prior to starting ciprofloxacin and until 7 days after completion of all doses of ciprofloxacin on study.

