8.2 Period of Observation

For the purpose of this study, the period of observation for adverse events starts on the day the subject signs informed consent. For subjects who fail screening, the period of observation ends on the date of screening failure. Treated subjects, including those who were prematurely discontinued from the study, will be followed for any adverse events that occur during the study from the time the subject signs the informed consent form until 28 days (± 7 days) following the last dose of study treatment (i.e., the Follow-up Visit). However, if another course of anti-cancer therapy is initiated prior to the 28-day follow-up period visit, collection of adverse events will no longer be performed, with the exception of events that may be possibly, probably, or definitely related to the investigational agent or are clinically significant.

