11.2.2 Dose Limiting Toxicity Evaluable Population (Phase Ib)

Subjects withdrawn before C1D1 will not be evaluable for dose escalation decisions and will be replaced. A subject is evaluable for dose-escalation decisions provided: they receive all drug doses and remain on study until evaluation at Cycle 1 Day 28 without a DLT; or they experienced a DLT during Cycle 1. Subjects who miss any etoposide or ciprofloxacin doses or

withdraw from study without a DLT and prior to Cycle 1 Day 28 are not evaluable and will be replaced in their cohort of treatment. Tabulations of DLTs will only include the DLT-evaluable population.

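### The safety population requires a dose of each drug, so a subject who stops after ciprofloxacin alone drops out of the adverse event summaries although the events are collected

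*Combined protocol and SAP*

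**What the plan says.** Section 11.2.1 sets two conditions. The safety population is "all subjects who received at least one dose of each study drug and had at least one post-dose safety assessment", and "Safety summaries will include all subjects in the safety population". Section 11.3.1 then promises summaries of all adverse events, serious adverse events, treatment-related events and events leading to discontinuation.

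The two drugs do not start together. Section 4.1 states: "Ciprofloxacin will be administered orally twice daily on Days 1 to 10 of each 28-day cycle", and "Etoposide at a fixed dose of 200 mg will be administered orally once daily on Days 2 to 8 of each 28-day cycle". Section 3.2.2 gives the reason (a steady state before etoposide) and confirms that "ciprofloxacin will be started 24 hours before etoposide is begun".

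The rules for collecting events are wider than the population. Table 1, footnote 11: "Subjects who have received at least one dose of study drug and discontinue prematurely (regardless of reason) will be followed for any adverse events". Section 8.2: "Treated subjects, including those who were prematurely discontinued from the study, will be followed for any adverse events that occur during the study". In Phase Ib, Section 11.2.2 makes subjects evaluable for dose escalation if they complete Cycle 1 with all doses taken, "or they experienced a DLT during Cycle 1". It does not ask for a dose of each drug.

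**The concern.** Every subject passes through about 24 hours on ciprofloxacin alone. That period becomes longer if etoposide is delayed, and it has no end if etoposide is never taken. A subject who stops in it fails the first condition of Section 11.2.1. One likely reason for stopping that early is a reaction to ciprofloxacin, which is the drug whose dose Phase Ib escalates. The analysis set can therefore lose subjects because of the toxicity it is meant to describe.

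The second condition raises a related difficulty. After Day 1 the next scheduled visit is Day 8 (±2 days), and eligibility asks only for a life expectancy of at least 4 weeks. A subject who took both drugs and then died or was lost before that visit might have no post-dose assessment. The plan does not say what counts as one.

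At stake is the incidence of Grade 3 or higher adverse events, a secondary objective in Section 2.2, together with the agreement between the DLT table and the adverse event tables.

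**Working it through.** The plan states no figure on this point, so there is none to reproduce. The check has three parts.

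**1. Can the same subject be a DLT and be outside the safety population?**

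Inputs (Section 4.1): ciprofloxacin twice daily for 10 days = 20 doses per cycle, two of them on Day 1; etoposide once daily on Days 2 to 8 = 7 doses, none on Day 1.

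- Stop after both Day 1 ciprofloxacin doses: 18/20 = 90% of ciprofloxacin missed.
- Stop after one dose: 19/20 = 95% missed.
- Etoposide in either case: 7/7 = 100% missed.

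DLT criterion 2 in Section 3.3.2 is met when a treatment-related effect causes more than 25% of either drug to be missed. A treatment-related stop on Day 1 in Cycle 1 of Phase Ib meets it. The subject is then DLT-evaluable under Section 11.2.2 and can move the dose decision, yet has taken no etoposide and is outside Section 11.2.1. Criterion 5 (QTc) is also counted from the start of ciprofloxacin. The opening sentence of Section 3.3.2 refers to treatment with both drugs, but criteria 2 and 3 name either drug and criterion 5 names ciprofloxacin alone.

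**2. How far does the incidence move?**

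Let N be the number treated with any study drug, and x the number with an event among the other N - 1. One ciprofloxacin-only subject with an event is left out.

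- Incidence with the subject included: (x+1)/N
- Incidence as the plan is written: x/(N-1)
- Fall: (x+1)/N - x/(N-1) = (N-1-x) / [N(N-1)]

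The fall is greatest at x = 0, where it equals 1/N, and shrinks to 0 when all the others have an event (x = N-1).

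The documents give no rate of stopping after ciprofloxacin alone, so N and x below are assumptions:

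| N | x | Any dose | Dose of each drug | Fall (points) |
|---|---|---|---|---|
| 6 | 1 | 2/6 = 33.3% | 1/5 = 20.0% | 13.3 |
| 14 | 3 | 4/14 = 28.6% | 3/13 = 23.1% | 5.5 |
| 30 | 6 | 7/30 = 23.3% | 6/29 = 20.7% | 2.6 |
| 30 | 20 | 21/30 = 70.0% | 20/29 = 69.0% | 1.0 |

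The last row matters because Section 1.2 reports grade 3/4 neutropenia in about two thirds of patients on oral etoposide. If Grade 3 or higher events of any kind are that common here, one omitted subject hardly changes the overall incidence.

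**3. Does it always go down?**

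No. If the excluded subject had no event, x/N becomes x/(N-1) and the estimate rises. With N = 14 and x = 3, 3/14 = 21.4% becomes 3/13 = 23.1%. If nobody stops after ciprofloxacin alone, nothing changes.

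**The case against.** The best defence is that the trial studies a combination, so a safety set exposed to both drugs is a reasonable choice, and that almost nobody will stop within a day. The second half stands: the window is short and the number affected is probably zero or very few. The first half is weak. Day 1 ciprofloxacin is part of the regimen, and the plan itself collects these subjects' events and allows them to be DLTs.

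It can also be said that Section 11.2.1 does not confine the summaries to this population. But no other population is named for the adverse event tables, so an analyst following the plan would use this one.

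Several stronger readings are tempting and are not supported:

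- *The subject disappears from all safety output.* The DLT tabulation has its own population (Section 11.2.2), examination, vital sign and ECG data are listed by subject (Section 11.3.1), and events are reported to the safety committee during the trial (Sections 8.4.1 and 10). The gap is in the adverse event summaries.
- *The Phase II safety stop could fail to trigger, with 5/14 turning into 4/13.* Section 9.3 does not refer to the safety population, and Section 9.2 replaces Phase II subjects withdrawn before one full cycle. The documents do not lead to that count.
- *Each omitted subject costs 1/N.* That is the maximum, reached only when no other subject has an event.
- *A QTc event is the typical case.* No ECG is scheduled between screening and Day 8, and Section 4.4.1.2 needs two separate ECGs for Grade 3, so detection on Day 1 would need unscheduled recordings.
- *Anyone who dies before the first visit is removed.* Death is itself a recorded Grade 5 event. Since the term for the assessment is undefined, such a subject may or may not be dropped.

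**Conclusion.** The point holds in a narrow form. As written, Section 11.2.1 leaves a subject who received only ciprofloxacin out of the adverse event summaries, while Table 1 footnote 11 and Section 8.2 collect that subject's events. In Phase Ib, Sections 3.3.2 and 11.2.2 can count one of those events as a DLT. The DLT overlap does not extend to Phase II.

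The size depends on assumptions that the documents do not settle. With one excluded subject who had an event, the fall in the Grade 3 or higher incidence ranges in the examples from 13.3 points in a group of 6 to 1.0 point in a group of 30 with common events. A reader might infer a general downward bias. That follows only when the excluded subjects had events; early stops for other reasons, such as withdrawn consent, push the estimate the other way. The response analysis and the two-stage design are not touched.

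**What to change.** Amend Section 11.2.1 so that the safety population is all subjects who received at least one dose of either study drug, with no condition on a later assessment. State in Section 11.3.1 that all adverse event summaries use this population. A short line giving the number who received ciprofloxacin only would show the reader whether the change mattered.

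The cost is a sentence or two. The events are already collected, so no extra data are needed, and neither the sample size nor the two-stage design changes.

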11.2.2 Dose Limiting Toxicity Evaluable Population (Phase Ib)

Subjects withdrawn before C1D1 will not be evaluable for dose escalation decisions and will be replaced. A subject is evaluable for dose-escalation decisions provided: they receive all drug doses and remain on study until evaluation at Cycle 1 Day 28 without a DLT; or they experienced a DLT during Cycle 1. Subjects who miss any etoposide or ciprofloxacin doses or

withdraw from study without a DLT and prior to Cycle 1 Day 28 are not evaluable and will be replaced in their cohort of treatment. Tabulations of DLTs will only include the DLT-evaluable population.

11.2.3 Efficacy Evaluable Population

The efficacy population will include all subjects who receive at least 1 cycle of ciprofloxacin and etoposide and had at least one post-dose efficacy assessment.

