2.2 Secondary

In subjects with resistant AML, to

- Determine the safety and feasibility of treatment with ciprofloxacin and etoposide;
- Measure the response duration, progression-free and overall survival (PFS and OS respectively);
- Estimate the incidence of Grade ≥ 3 adverse events following treatment with ciprofloxacin and etoposide at the MTD.

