3.2 Inclusion Criteria

- A. Age \geq 18 years.
- B. Diagnosis of AML confirmed by review of bone marrow pathology at the University of Florida.
- C. Patients with relapsed and or refractory AML
 - who failed to achieve CR or CRi after at least one cycle of induction chemotherapy and not suitable for second cycle of standard intensive chemotherapy,
 - who have progressed after 1 cycle of HMA or intolerant to HMA therapy and not suitable for standard induction chemotherapy regimens.
 - who have relapsed after any duration of response,
- D. Per the treating physician, the subject must have a life expectancy of \geq 4 weeks.
- E. Subject performance status must be Eastern Cooperative Oncology Group (ECOG) 0, 1, or 2 (see [Appendix B](#)).
- F. Subject must have total bilirubin \leq 2 mg/dL and AST and ALT \leq 2.5 times the upper limit of normal.
- G. Subject must have serum creatinine $<$ 2 mg/dL.
- H. Females of child-bearing potential (*i.e.*, women who are pre-menopausal or not surgically sterile) may participate, provided they meet the following conditions:
 - Must agree to use physician-approved contraceptive methods throughout the study and for 6 months following the last dose of ciprofloxacin and/or etoposide. Adequate forms of contraception are abstinence, double-barrier methods (*e.g.*, condoms with spermicidal jelly or foam and diaphragm with spermicidal jelly or foam), oral, depot, or injectable contraceptives, intrauterine devices, and tubal ligation.

- Must have a negative serum pregnancy test within 7 days prior to beginning treatment on this study.
- I. Males with female partners of child-bearing potential must agree to use physician-approved contraceptive methods (*e.g.*, abstinence, condoms, vasectomy) throughout the study and should avoid conceiving children for 6 months following the last dose of ciprofloxacin and/or etoposide.
- J. Subjects must have provided written informed consent and be willing to comply with all study-related procedures.

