7.1.2 Efficacy Data

The efficacy outcomes of interest will be CR (including CRi and CRp) as defined in [Appendix A](#). The efficacy variables, which will be used to assess response, include hemoglobin, ANC, platelets, circulating blasts, bone marrow aspirate and biopsy.

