9.2 Replacement of Subjects

Subjects who are withdrawn prior to C1D1 for any reason will be replaced.

Phase Ib - Subjects who withdraw or are withdrawn from study prior to C1 Day 28 without a DLT will be replaced by another subject.

Phase II - Subjects who withdraw or are withdrawn prior to receiving one full cycle of therapy will be replaced by another subject.

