11.3.2 Efficacy

All efficacy endpoints will be summarized descriptively using frequency distributions. In addition, 95% confidence intervals will be provided for the proportion of each response/improvement.

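### No analysis set is named for OS and PFS; by default they fall to the only efficacy set, which leaves out the earliest deaths and biases OS upward

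*Combined protocol and SAP*

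**What the plan says.** Section 2.2 and the synopsis list duration of response, PFS and OS as secondary objectives.

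Section 11.2 defines three analysis sets:

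- **Safety (11.2.1):** at least one dose of each drug and a later safety assessment. Its stated use is safety summaries.
- **DLT-evaluable (11.2.2):** Phase Ib only. Its stated use is DLT tabulation.
- **Efficacy (11.2.3):** all subjects who receive "at least 1 cycle of ciprofloxacin and etoposide and had at least one post-dose efficacy assessment".

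Section 11.3.2 names no population and no time-to-event method: "All efficacy endpoints will be summarized descriptively using frequency distributions". Section 7.1.2 says "The efficacy outcomes of interest will be CR (including CRi and CRp) as defined in" Appendix A; it does not mention OS or PFS. It adds that the variables used to assess response "include hemoglobin, ANC, platelets, circulating blasts, bone marrow aspirate and biopsy".

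Section 4.1 says that "those in Phase II will be considered evaluable for response if they have received at least one cycle in accord with the protocol". Section 9.2 says, for Phase II, "Subjects who withdraw or are withdrawn prior to receiving one full cycle of therapy will be replaced by another subject". Nothing says whether a replaced subject stays in any survival analysis. Section 6.4 has all subjects followed monthly to progression, death or 3 years.

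**The concern.** Entry to the efficacy set depends on what happens after treatment starts. A subject who dies during the dosing days cannot have received a cycle and is left out. A subject who lives through them is included and keeps those days as survival time. If OS is computed in that set, the earliest deaths are missing from the curve and the estimate is too high.

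Early losses are foreseeable. Section 3.2 requires that "the subject must have a life expectancy of" at least 4 weeks, which is the length of one cycle. Section 11.1 itself allows for 20% dropout.

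The trial has one arm, so its OS and PFS can be interpreted only against outside experience. That requires a clear denominator and time origin, and the plan states neither for these endpoints. The problem is separate from how the 14 and 24 response-evaluable subjects are counted, and settling that count for CR would not resolve it.

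**Working it through.** **The plan's own figures.** Section 11.1 gives no survival figure, but it gives the numbers needed for a bound.

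- Two-stage rule: stop if 2 or fewer of 14 respond; reject 20% if 8 or more of 24 respond. The exact binomial calculation gives type I error 0.0874 and power 0.8024 at 40%, within the stated 0.10 and 80%.
- Dropout: 24/(1 - 0.20) = 30. So 30 - 24 = 6 planned Phase II subjects fall outside the evaluable set.

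Both reproduce.

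**Bound without an assumed median.** Let k of the 6 excluded subjects be early deaths. Assume that no early deaths remain in the set and that the other 6 - k exclusions are unrelated to survival. After the early period 30 - k subjects are alive, and the 24 analysed behave like a random sample of them. Hence

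S_evaluable(t) = S_all(t) × 30/(30 - k).

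| k | Factor | A true 40% would read as |
|---|---|---|
| 0 | 30/30 = 1.00 | 40% |
| 3 | 30/27 = 1.11 | 44% |
| 6 | 30/24 = 1.25 | 50% |

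**Effect on median OS, with assumed medians.** The documents give no survival figure, so I take exponential OS from Day 1 with a true median m of 3 to 6 months. This is an assumption. If deaths before time w are removed:

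- share removed = 1 - 2^(-w/m);
- by the memoryless property, the median measured from Day 1 among the rest = m + w.

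The window w depends on what receiving one cycle means, which the plan does not define. The dosing days give w = 10/30.44 = 0.33 months. The whole cycle gives w = 28/30.44 = 0.92 months.

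| Window | m (months) | Share removed | Of 30 | Apparent median (months) | Increase |
|---|---|---|---|---|---|
| 10 days | 3 | 7.3% | 2.2 | 3.33 | 11% |
| 10 days | 6 | 3.7% | 1.1 | 6.33 | 5% |
| 28 days | 3 | 19.1% | 5.7 | 3.92 | 31% |
| 28 days | 6 | 10.1% | 3.0 | 6.92 | 15% |

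The two calculations agree in scale: the 28-day rows correspond to k of about 3 to 6.

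**PFS.** The calculation covers death only. Marrow is scheduled at Day 28 (sections 6.2 and 7.2.1). A subject found to have progressed then has received a cycle and stays in the set. The month figures therefore do not carry over to PFS.

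**The case against.** The strongest objection is that the plan never says OS and PFS are estimated in this set. A reader might infer that they would be estimated only in subjects who completed a cycle and had a later assessment. The documents do not support that reading. Section 7.1.2 lists only CR, CRi and CRp as efficacy outcomes, section 11.3.2 names no population, section 4.1 limits evaluability to response, and section 6.4 follows everyone. Section 11.2.3 also speaks of receiving a cycle and of an assessment after dosing, not after the cycle. Blood counts are among the response variables and are taken on Day 8, so the assessment condition can be met in the first week, and deaths on Days 11 to 28 may be retained. All of this stands. What remains is that no other set is offered for survival, and deaths during the dosing days are lost on either reading.

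Second, the life-expectancy criterion screens out patients expected to die within 4 weeks. That works against a constant hazard from Day 1, so the 28-day figures may be too high. This also stands, although the screen is a physician's prediction and will be imperfect.

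Third, OS and PFS are secondary and descriptive, with no test or decision attached. That limits the consequence but does not remove the bias.

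Fourth, section 6.4 read literally ends follow-up at progression, so later deaths may not be captured in any population. This is a separate limit on OS that changing the analysis set does not cure.

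**Conclusion.** The point holds as a conditional one. The plan names no population, time origin or estimation method for OS and PFS, and the only efficacy set conditions on early survival. Used by default, it biases OS upward and may bias PFS by an amount not shown here.

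For OS, the inflation of S(t) runs from none to a factor of 1.25, depending on how many of the 6 planned non-evaluable subjects are early deaths. Under the assumed 3 to 6 month exponential medians, the median rises by about 0.33 months (5 to 11%) on the dosing-days reading and by up to 0.92 months (15 to 31%) on the 28-day reading.

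The bound uses the 30 subjects of section 11.1. The section on number of subjects allows up to 44 in Phase II. With 24 evaluable, that would put 20/44 = 45% outside the set, so the two enrolment figures need reconciling.

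This should be corrected, as a matter of secondary endpoints; it does not affect the CR test.

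**What to change.** Add to sections 11.2 and 11.3.2: OS and PFS are estimated by Kaplan-Meier from Cycle 1 Day 1 in all subjects who received any dose of either study drug; deaths before the first response assessment count as events; subjects replaced under section 9.2 remain in these analyses. Keep the section 11.2.3 set for response summaries only.

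The existing safety population is not a substitute. It requires a dose of each drug, and etoposide starts on Day 2, so a subject who dies after ciprofloxacin alone would be missing.

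The cost is a few sentences, and the survival figures become less favourable. No extra visits are needed to count the early deaths, because section 6.4 already follows all subjects. The two-stage boundaries are unchanged. The same edit should make clear whether deaths after progression are collected, since OS depends on that in any population.
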